Additional hemodynamic endpoints: While the primary endpoint will be difference in norepinephrine dose at 6h, we will also measure the difference in vasopressor dose between groups at 12h and over time using mixed linear model (see data analysis). We will also measure differences in heart rate at the 6 and 12h time points and over time (see data analysis). Other secondary hemodynamic endpoints will include time to shock reversal (cessation of all vasopressors for at least 12h) and change in lactate over time (0, 6, 12, 24 h).

Oxygen consumption: Aim #2a endpoint will consist of difference in oxygen consumption over time between esmolol and control groups. Based on findings in the Morelli *et al.* study, we anticipate a similar decrease in VO_2 among those who receive esmolol. While Morelli *et al.* measured VO_2 via PA catheter, we will measure VO_2 directly via the ventilator.

Inflammatory endpoints: For Aim #2b, we will characterize the effects of esmolol infusion on the inflammatory cascade as measured by changes in select inflammatory biomarkers at time points 12 and 24 hours accounting for baseline measurements at time zero.

Clinical endpoints: Recognizing that we lack power to detect differences in mortality, we will still collect in-hospital mortality anticipating that if the overall study is positive, we can use these data to help power a future Phase III trial. In addition, we will measure the clinical endpoints of length of ICU stay, hospital length of stay, and organ dysfunction at 96 hours as defined with the SOFA score.

Data acquisition and management: [name] and the Center for Resuscitation Science have extensive experience in data collection, data entry, database development, and data management for both large-scale observational trials and randomized clinical trials. The Center for Resuscitation Science currently manages over 20

active databases with over 1 million data points from nearly 10 years of research. As such, we have honed an effective and reliable protocol for managing data as described below.

Data Entry and Quality:

Immediately following data collection, the paper data sheet will be entered directly into the electronic database REDCap (described below). Two trained research assistants will independently enter the data for primary and secondary endpoints to ensure transfer accuracy. Several measures are taken to assure data quality. They are as follows:

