The association between continuous infusion of esmolol and need for vasopressor support was assessed by comparing the median 6 hour norepinephrine equivalent dose (NED) between groups using a Wilcoxon rank-sum test. No patients expired prior to 6 hours after enrollment. To analyze the difference in vasopressor dose between groups at 12 hours and over time, we compared NED (recorded hourly for 12 hours) over time between groups using linear mixed effect models accounting for repeated measures and adjusting for pre-intervention NED. The appropriate variance-covariance structure was selected based on Akaike information criterion. Using this model, we tested whether NED was different at 12 hours and for differences in the overall trend over time. A similar analysis was used to assess the difference in heart rate between groups over the first 12 hours and lactate between groups over the first 24 hours; however, in the heart rate analysis, we tested for mean differences at 6 hours, 12 hours and for differences in the overall trend over time, and in the lactate analysis, we used a log-transformed lactate value to test for mean differences at 12 and 24 hours and for differences in the overall trend over time. We compared the median number of shock free days, defined as cessation of all vasopressors during the first 7 days, between the two groups.

To characterize the effects of esmolol infusion on VO_2 , we limited the analysis to patients who were mechanically ventilated during the study period. The VO_2 values were cleaned based on a custom algorithm that eliminated points that met any of the following four criteria: 1) VO_2 value corresponding to a Fraction of Inspired Oxygen (FiO_2) value above 61%. 2) VO_2 value within 10 minutes of a 10-unit change in FiO_2 . 3) VO_2 value above 800 mL/kg/min or below 80 mL/kg/min that is not sustained for at least 30 consecutive minutes. 4) VO_2 value that is 15% higher or lower than the average of the VO_2 values 5 minutes before and after the point in question.

To analyze the difference in oxygen consumption between groups at 12 hours, 24 hours and over time for patients who were on mechanical ventilation at enrollment, we compared VO_2 measurements (standardized by bodyweight in kilograms) over time (recorded every minute

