from the time of study drug administration over a period of at least 24 hours) between groups using mixed linear model accounting for repeated measures (n = 15). We did not adjust for pre-intervention VO₂ measurements. Using this model, we tested for mean differences at 12 hours, 24 hours and for differences in the overall trend over time. The appropriate variance-covariance structure was selected based on Akaike information criterion. Additionally, a figure was created by first computing the mean of all the VO₂ observations for a patient by timepoint, and then computing the mean of the means for each timepoint by treatment group.

To characterize effects of esmolol on inflammatory markers in patients with vasopressor-dependent septic shock, we compared log-transformed values of biomarkers at 12 and 24 hours and over time between groups using mixed linear model accounting for repeated measures and adjusting for pre-intervention biomarkers. The appropriate variance-covariance structure was selected based on Akaike information criterion.

In-hospital mortality was compared between groups using the Fisher's Exact test. Baseline covariates appeared to be balanced, so we did not adjust for any additional covariates. Length of hospital and ICU stay was compared between groups using a Wilcoxon ranked sum test and stratified based on hospital survival. To characterize effects of esmolol on SOFA score over the first 24 hours, we compared SOFA at 6, 12, and 24 hours and over time between groups using a mixed linear model accounting for repeated measures and adjusting for pre-intervention SOFA.

All analyses were conducted using Stata 14.2 (College Station, TX) and a p-value of <0.05 was considered significant.

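### The VO2 mixed model rests on 15 patients but states no small-sample reference distribution, does not secure patient-specific slopes, and runs three tests at 0.05; refit it, pair it with a patient-level Welch comparison, and label VO2 exploratory

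*SAP*

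**What the plan says.** The protocol (Secondary endpoints, Oxygen consumption) defines the endpoint in general terms: "Aim #2a endpoint will consist of difference in oxygen consumption over time between esmolol and control groups". It gives no time point, window or parameter.

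The SAP (Statistical Analyses) first removes readings: VO2 values were "cleaned based on a custom algorithm that eliminated points that met any of the following four criteria". It then compares body-weight-standardised readings "for patients who were on mechanical ventilation at enrollment", one per minute from the start of study drug "over a period of at least 24 hours) between groups using mixed linear model accounting for repeated measures (n = 15"). There is no adjustment for pre-intervention VO2. On the covariance it says: "The appropriate variance-covariance structure was selected based on Akaike information criterion". On the tests: "Using this model, we tested for mean differences at 12 hours, 24 hours and for differences in the overall trend over time". For every analysis, "a p-value of <0.05 was considered significant".

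The SAP does not give the estimation method, the degrees-of-freedom method, the list of covariance candidates, the number of patients per arm or any ranking of the three VO2 tests.

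**The concern.** A day of one-minute readings gives about 1,440 records per patient, roughly 21,600 in all before cleaning. Those records describe each patient's curve closely, but the comparison between arms is still a comparison of 15 people. Three things follow.

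- **Reference distribution.** With about 13 degrees of freedom, the normal distribution is too narrow. AIC selects a covariance pattern; it does not correct the distribution against which the test statistic is judged.
- **Patient slopes.** AIC can select patient-specific slopes only if they were among the candidates, and the candidates are not listed. If patients drift at different rates and the model has no term for it, the standard error of the trend is too small, and changing the degrees of freedom does not repair that.
- **Three tests.** Each is judged at 0.05, and the SAP does not say which one answers Aim 2a.

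At stake is whether a chance difference in a small ventilated subset could be reported as an effect of esmolol on oxygen consumption.

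**Working it through.** **The plan's own design figure.** The only sample size in the documents is for the primary endpoint: difference 0.05, SD 0.09 mcg/kg/min, 80% power, 0.05 type I error (taken as two-sided). The normal formula gives 2 × (1.960 + 0.842)² × (0.09/0.05)² = 50.9, so 51 per arm. The exact t calculation gives 52 per arm with power 0.801, hence 104, as stated. No design figure is given for VO2.

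**Inputs for VO2.** From the SAP: 15 patients, two arms, three tests, threshold 0.05. Assumed, because the documents do not give them: the arm split (8/7 to 11/4), all variance components, and whether z or t was used.

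**Error of one z test on 15 patients.** Degrees of freedom are 15 − 2 = 13.
- REML variance: 2 × P(T13 > 1.960) = 0.072.
- ML variance, too small by a factor of 13/15: 2 × P(T13 > 1.960 × √(13/15)) = 2 × P(T13 > 1.825) = 0.091.

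Simulating 24 hourly means per patient with no effect (8 vs 7, 40,000 runs, patient slopes in the model) gives 7.0–7.4% for REML with z, 8.9–9.3% for ML with z, and 4.8–5.1% for REML with t on 13 degrees of freedom.

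**Chance of at least one false positive in three tests.** If the tests were independent: 1 − 0.95³ = 14.3%. They are correlated, so the simulated figure with t on 13 degrees of freedom is 10.2–10.4%. A minute-level simulation (1,441 minutes, random intercept and slope, AR(1) noise, REML, 2,000 null trials per setting, Monte Carlo error about 0.5 points) gives:

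| Reference | Per test | At least one of three |
|---|---|---|
| z | 5.8–7.2% | 13.6–14.5% |
| Satterthwaite | 4.0–4.9% | 9.4–10.6% |

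The fitted model was fixed in these runs; an AIC selection step was not simulated.

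**Omitted patient slopes.** In the hourly simulation (intercept SD 1, noise SD 0.5), a random-intercept-only model gives the trend test an error of 5.1% when the true slope SD over 24 h is 0, 24.1% when it is 0.5 and 45.8% when it is 1. Using t on the residual degrees of freedom barely changes this (24.0% and 45.7%). In the minute-level setting, random intercept plus AR(1) without slopes gives 15.9–38.2% (ML, z). The size depends entirely on the assumed slope variance.

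**Unequal variances.** Suppose the smaller arm has twice the SD:

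| Split | Satterthwaite model, per test | Welch on patient summaries, same runs |
|---|---|---|
| 10 vs 5 | 10.4–10.8% | 4.1–5.9% |
| 11 vs 4 | 13.4–13.8% | 4.5–6.0% |

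A separate larger run of a single test on patient summaries gives 11.7% and 15.0% for the pooled t test, against 5.5% and 6.1% for Welch.

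**Precision.** The difference detectable with 80% power (equal SDs) is 1.57 SD at 8 vs 7, 1.66 at 10 vs 5 and 1.77 at 11 vs 4.

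**Is the slope the natural main contrast?** Suppose a constant reduction begins at fraction c of the 24 h. The least-squares slope over 24 h then recovers 6c(1 − c) of it. For an assumed onset at 1 h, 6 × (1/24) × (23/24) = 24%; at 2 h, 6 × (2/24) × (22/24) = 46%. A rapid, sustained fall in VO2 would show mainly as a difference in level, not in slope.

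**The case against.** The strongest reply is that no error has been shown. The SAP does account for repeated measures, so a reader who infers that minutes were treated as independent is not supported by the text. A reader might also infer that the VO2 p-values are inflated because z tests were used. The documents do not say so: naming the software does not fix the reference distribution, and the actual inflation is unknown. If z tests were used with REML and a correct covariance, the excess is only about 2 points per test. All of this stands.

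Two further replies stand in part. First, heart rate and lactate are also tested with three unranked contrasts each, so multiplicity is not peculiar to VO2; what is particular here is its combination with 15 patients. Second, VO2 is a secondary, mechanistic aim of a pilot trial. That limits the weight of the point, but Aim 2a is a named specific aim and its p-values should be interpretable.

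A tempting remedy is to read the protocol's wording as the 0–24 h arm-by-time slope and make that the main contrast. The documents do not support this. The endpoint wording does not say whether a level, a slope or a group-by-time test is meant. The protocol's purpose section hypothesises lower VO2 and cites an earlier trial in which VO2 was lower at every measured time. The SAP is also written in the past tense and already reports the 15 patients, so ranking the contrasts now would be post hoc and would not restore a 5% error rate.

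Nor do corrected degrees of freedom suffice alone: the Satterthwaite model fails under unequal variances almost as badly as a pooled t test.

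**Conclusion.** The point holds as a defect in how the VO2 comparison is specified, not as proof of a wrong result. What needs no assumption is that the arm contrasts rest on 15 patients, no small-sample reference is stated, patient slopes are not assured, and three tests share one threshold without ranking.

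The sizes are conditional. The 7% (REML) and 9% (ML) per-test errors require z inference. The 16–46% trend errors require omitted slopes and the assumed slope variances. The roughly 10% chance of at least one false positive applies even when each test is valid, under the simulated correlations. With detectable differences of 1.57 to 1.77 SD, the analysis can support only an exploratory reading. The primary analysis and N = 104 are not touched. The issue should be corrected, at moderate weight.

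**What to change.** 1. Refit the VO2 model by REML with a patient random intercept and slope required, not left to AIC, plus serial correlation. Use Kenward-Roger or Satterthwaite degrees of freedom. State these choices and the covariance candidates.
2. Alongside it, compare one summary per patient by Welch t test: mean VO2 over stated windows (for example 11–13 h and 22–24 h) and the patient's slope. Give this at least equal weight, because neither the arm split nor the arm variances are given. Avoid a pooled t test for the same reason.
3. Report patients per arm, patients with cleaned readings in each window, and 95% confidence intervals.
4. Label all three contrasts exploratory and do not name the slope as main. Disclose that the windows, and any ranking of contrasts, were set after the data were known.

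**Cost.** SAP wording and a rerun on existing data. Intervals become about 10% wider than z intervals with REML variance (2.160/1.960 = 1.10) and 18% wider than z intervals with ML variance (1.102 × √(15/13) = 1.18). Patients with no cleaned readings in a window drop out of the patient-level comparison; with 11 left (6 vs 5), the detectable difference rises from 1.57 to 1.91 SD. Welch is not exact either: it reached 6.1% at 11 vs 4 with twice the SD in the smaller arm. Sample size and the primary analysis do not change. The SAP's two descriptions of the ventilated population are a separate point.

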2.1a. Esmolol is associated with reductions in heart rates in patients with septic shock Morelli *et al.*⁶ conducted an open-label randomized Phase II trial of esmolol for patients with septic shock who had a heart rate >95/min and received high dose norepinephrine to maintain a mean arterial pressure (MAP) >65mmHg. The investigators randomly assigned 77 patients to esmolol and 77 to standard care, with a primary outcome of reduction of heart rate to 80-94/min for 96h. Secondary outcomes included organ dysfunction as well as mortality. They found that they were able to achieve heart rate control in all patients in the esmolol group without adverse effects. In what has received the most attention in the critical care community, 28 day mortality was 49.4% in the esmolol group vs 80.5% in the control group (hazard ratio, 0.39; 95% CI, 0.26 to 0.59; $P < .001$). *While these results appear promising, the study cohort may not represent a typical septic shock population in a United States ICU. For example:*

- 1) The control group had a 28-day mortality of 80.5% and an overall in-hospital mortality of 90.9% which is much higher than typical mortality related to septic shock seen in the U.S. (generally 25-50% in most U.S. ICUs).^{19, 20}
- 2) All of these patients had pulmonary artery catheters (PACs) which are not routinely used in the care of septic shock patients in most ICUs
- 3) The study patients were receiving what would be considered high doses of norepinephrine in most U.S. ICUs (the median dose of norepinephrine in the study was 0.38 mcg/kg/min [0.21-0.87] in the esmolol group and 0.40 [0.18-0.71] in the control group)
- 4) All study patients received hydrocortisone (300mg/day) which is not routine for all cases of septic shock in most U.S. ICUs
- 5) Study patients who had a mixed venous oxygen saturation <65% or increasing arterial lactate concentration were treated with levosimendan, a non-adrenergic calcium

sensitizer aimed at improving systemic oxygen delivery which is not used clinically in the United States

For these reasons, *it is essential to reproduce this trial in a critical care environment in the United States before larger scale trials could be advocated.*

2.1b. Use of esmolol in septic shock appears to be safe and well-tolerated

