Consent: If a patient meets all of the inclusion criteria and none of the exclusion criteria, a member of the research team will approach the patient for written informed consent. If the patient is unable to consent, a legally authorized surrogate may be approached per standard IRB procedures. Investigators will explain the study's background and significance, potential risks and benefits, and study protocol. In the event that a physician Investigator or a surrogate is not physically present in the hospital to perform the consent process, a non-physician study staff (research assistant or research coordinator) will coordinate a conference (i.e. FaceTime or Skype video conferencing or telephone) for the physician investigator / surrogate to join in the consent discussion. If consent is obtained, a signed copy will be given to the patient and another copy placed in the medical record. The original signed informed consent will be kept in our locked research office (see specifics in **Section B6 - Recruitment and Consent Procedures**).

Randomization: The randomization will be done in a 1:1 ratio between treatment and control groups in varying blocks of two to six using SAS software. This main list of group assignment will be maintained in the hospital research pharmacy.

Study Arms: After randomization as described above, patients will be assigned to one of the following two arms: esmolol for 24 hours or standard care (no esmolol).

1) Esmolol for 24 hours: Patients in this arm of the study will have Esmolol for 24 hours.

2) "Usual Care": Patients will receive 100 mL of normal saline over 5-10 minutes at the beginning of the study in addition to usual care. When patients are enrolled in a clinical trial there is a time period from consent to study drug administration that depends on the investigative team, the research pharmacy, and the available nursing staff. In order to guarantee that this time interval is similar between the two groups the control arm will receive a small bolus of saline at the beginning of the trial. This will ensure that "time zero" is similar between the two groups.

Blinding: The study will not be blinded as an esmolol infusion must be actively titrated to effect by clinicians and it will noticeably decrease heart rate.

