Esmolol to Treat the Hemodynamic Effects of Septic Shock

NCT02369900

December 3, 2020

Statistical Analyses

Preliminary observational data on a cohort of septic shock patients indicated a mean norepinephrine equivalent dose was 0.15 ± 0.09 mcg/kg/min at the 6 hour time point. We anticipated a 33% reduction in mean norepinephrine dose to 0.10 ± 0.09 mcg/kg/min after 6 hours of continuous treatment with esmolol. Based on these estimates, for a two-sample t-test with a power of 80% and a type I error of 0.05, we estimated that a total of 104 patients would be required to show a statistically significant difference between treatment and control groups.

Descriptive statistics are provided for baseline and outcome variables. Continuous variables are presented as means with standard deviations or medians with interquartile ranges (IQR), based on the distribution of the data. Categorical variables are presented as counts with percentages. In univariate analysis, continuous variables were analyzed using a Student's t-test if normally distributed and a Wilcoxon ranked sum test if non-normal. Categorical variables were analyzed using a Fisher's exact test.

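### Mortality is left unadjusted because the arms looked balanced, which is not a sound reason, and the SAP names no mortality effect measure or confidence interval

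*SAP*

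**What the plan says.** The mortality analysis in the SAP (Statistical Analyses) is one test: "In-hospital mortality was compared between groups using the Fisher's Exact test". The next sentence gives the only reason for leaving it unadjusted: "Baseline covariates appeared to be balanced, so we did not adjust for any additional covariates". There is no covariate list, no definition of balance and no adjusted sensitivity analysis. The general paragraph on descriptive statistics does provide counts and percentages for categorical outcomes, so deaths by arm will be shown. No risk difference, ratio or confidence interval is named for mortality.

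Elsewhere the SAP adjusts for the baseline value without reference to balance, in the models for vasopressor dose, biomarkers and SOFA and, by cross-reference, heart rate and lactate. It does not do so everywhere: the VO2 model is explicitly unadjusted. Baseline SOFA is available, because the protocol (B3.A, Measurements) has it calculated at every time point and the SAP uses it in the SOFA model.

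On the role of mortality, the protocol (B3.A, Clinical endpoints) is frank: "Recognizing that we lack power to detect differences in mortality, we will still collect in-hospital mortality". It adds that "if the overall study is positive, we can use these data to help power a future Phase III trial". The protocol text available for this review contains no adjustment rule for mortality.

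**The concern.** A covariate earns its place in a model by predicting the outcome, and that can be judged before any data are seen. Balance is a different matter. Passing a balance check still leaves some residual imbalance. Even where balance is close to exact, an unadjusted standard error ignores the outcome variation that the covariate explains. A rule that adjusts only when the arms look different therefore forgoes most of the available benefit, and with no stated criterion it cannot be reproduced.

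What is at stake is how useful the mortality result is. For an endpoint that the trial admits it cannot test with adequate power, the informative output is an estimate with an interval. A later planner would need that more than a p-value, and the SAP does not name one.

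**Working it through.** **1. The plan's own figure.** Inputs from the SAP: means 0.15 and 0.10, SD 0.09, power 80%, type I error 0.05 (sidedness not stated; taken as two-sided).

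Normal approximation: n per arm = 2 × (1.960 + 0.842)² × 0.09² / 0.05² = 50.9, so 51 per arm and 102 in total. The exact t-test calculation gives 51.84, so 52 per arm and 104 in total, with power 80.1%. This reproduces "a total of 104 patients would be required". Allocation is 1:1 (protocol, Randomization), hence 52 per arm. No corresponding figure is given for mortality.

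**2. Unadjusted mortality interval.** The documents assume no mortality rate for this trial. I use the protocol's range for septic shock (section 2.1a), "generally 25-50% in most U.S. ICUs", which gives 26 to 52 deaths if all 104 patients are analysed.

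Half-width = 1.96 × √(2p(1−p)/52)
- p = 0.25: 1.96 × √(0.375/52) = 16.6 points
- p = 0.50: 1.96 × √(0.5/52) = 19.2 points

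**3. Gain from adjustment, by formula.** If baseline covariates explain a share R² of outcome variance, the variance of the risk difference is multiplied by about (1 − R²), and effective N is 104/(1 − R²). R² is not in the documents, so a range is shown.

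| Assumed R² | Half-width at 25% / 50% mortality (points) | Effective N |
|---|---|---|
| 0 | 16.6 / 19.2 | 104 |
| 0.05 | 16.2 / 18.7 | 109 |
| 0.10 | 15.8 / 18.2 | 116 |
| 0.20 | 14.9 / 17.2 | 130 |
| 0.30 | 13.9 / 16.1 | 149 |

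**4. Check by simulation.** Settings: 52 per arm, control mortality 25% or 50%, one normal covariate, conditional log odds ratio for treatment 0 or −0.8, 4,000 runs per scenario. The standardised risk difference from logistic regression was compared with the raw difference. Balanced means that the arms differed on the covariate by less than 1.96 standard errors.

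| Covariate odds ratio per SD | R² | Variance ratio, adjusted/raw | Interval narrower by (1 − √ratio) | Ratio in balanced trials only |
|---|---|---|---|---|
| 2.0 | 0.081–0.099 | 0.901–0.943 | 3–5% | 0.920–0.954 |
| 2.7 | 0.147–0.173 | 0.834–0.899 | 5–9% | 0.865–0.919 |
| 4.1 | 0.238–0.269 | 0.729–0.778 | 12–15% | 0.774–0.816 |

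Much of the gain survives in trials that pass the balance check. Adjusting only when the check fails leaves the variance ratio at 0.907 to 0.986, so most of the benefit is lost. Bias of the raw difference was at most 0.3 points.

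A separate simulation for a SOFA odds ratio of 1.5 to 2.5 per SD found the SD of the risk difference reduced by about 0 to 7%. That is at most 0.07 × 16.6 = 1.2 to 0.07 × 19.2 = 1.3 points of half-width.

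**5. The odds ratio behaves differently.** With no treatment effect, the SE of the log odds ratio rises on adjustment: from 0.463 to between 0.489 and 0.543 at 25% mortality, and from 0.396 to between 0.423 and 0.473 at 50%. The conditional effect moves further from zero, so any gain appears as power.

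**6. Power.** Assumed control mortality 40%, conditional odds ratio 0.4, 2,500 runs per scenario:

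| SOFA odds ratio per SD | Fisher | Unadjusted likelihood-ratio test | SOFA-adjusted | Due to SOFA alone (points) |
|---|---|---|---|---|
| 1.5 | 44.7% | 54.7% | 56.5% | 1.8 |
| 2.0 | 40.7% | 49.8% | 54.0% | 4.2 |
| 2.5 | 37.4% | 45.5% | 50.7% | 5.2 |

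Most of the rise comes from leaving Fisher's test, whose actual size at 52 per arm is 3.0% at 25% mortality and 3.9% at 50%. For a smaller effect of about 10 points (conditional odds ratio 0.62), unadjusted and adjusted power were 20.6% and 20.2%, 18.1% and 18.1%, and 18.5% and 20.7% at the same three SOFA strengths. The covariate then adds about 0 to 2 points.

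**The case against.** The best defence is that nothing here is invalid. Patients are randomised, so the simple comparison is unbiased. The endpoint is secondary and openly underpowered. Deaths and percentages by arm are reported, so any reader can compute a risk difference and interval, and the raw event rate remains usable for planning. The gain from SOFA is a point or so on a half-width of 17 to 19. The SAP, dated December 3, 2020, describes completed analyses, so a model added now is post hoc. The number enrolled is not given: at an illustrative 20 to 30 per arm, 25% to 50% mortality means only 10 to 30 deaths.

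All of that stands, and it limits the point. It does not make observed balance a reason to omit a prognostic covariate.

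Some stronger readings are tempting, and the documents do not support them:
- **The mortality result is biased, or the choice was steered by the outcome.** The SAP refers only to baseline covariates, and the unadjusted comparison is valid.
- **The plan yields nothing but a p-value.** Counts and percentages are promised.
- **Adjustment would lift power from about 41% to 54%.** Of those 13.3 points, 9.1 come from replacing Fisher's test, and the figure assumes a large effect.
- **Mortality is collected in order to plan Phase III.** The protocol offers this only as a possible aid, conditional on a positive study.

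**Conclusion.** The concern holds as a minor point in two parts. The stated rationale is unsound, because adjustment should follow prognostic strength and not observed balance. The more basic gap is that no effect measure or interval is named for mortality.

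The loss is small. For a SOFA odds ratio of 1.5 to 2.5 per SD, the risk-difference interval would be about 0 to 7% narrower. It would reach about 15% only with much stronger baseline prediction: the simulation gives that at R² 0.27, and the formula gives 1 − √0.70 = 16% at R² 0.30. These figures assume 52 per arm analysed, mortality of 25% to 50%, and a prognostic strength that the documents do not supply. With 30 per arm the unadjusted half-width would be 21.9 to 25.3 points, and with 20 per arm 26.8 to 31.0. The primary endpoint is unaffected.

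**What to change.** In the mortality paragraph of the SAP:
1. Keep Fisher's exact test as the simple comparison.
2. Report the risk difference in in-hospital mortality with a 95% CI.
3. Add, whatever the observed balance, one logistic regression of in-hospital death on arm and baseline SOFA. Report the standardised risk difference with a 95% CI, and give the adjusted odds ratio as supplementary because its SE rises with adjustment.
4. Label that model post hoc unless a document shows that it was specified before the data were seen.
5. Delete the sentence that justifies non-adjustment by balance.

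The cost is a few lines of text and one regression on data already collected. The downsides are one model assumption and a second mortality estimate to report. If far fewer than 104 patients were enrolled, deaths may be too sparse for the model to be reliable. In that case the unadjusted risk difference with its interval should carry the result.
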